# 2 PROPOSAL

A double-blind randomised controlled phase II trial of Tocovid SupraBio plus pentoxifylline (PTX) in patients suffering chronic gastrointestinal adverse effects of pelvic radiotherapy.

## 3 AIM

To test the benefits of oral Tocovid SupraBio (tocotrienols) with pentoxifylline (PTX) in patients suffering chronic gastrointestinal adverse effects following curative pelvic radiotherapy for cancer who have undergone maximal medical therapy after gastroenterological assessment using The Royal Marsden Hospital algorithm for managing GI late effects.

# 4 PATIENTS

Eligibility will be confirmed by a consultant in gastroenterology at The Royal Marsden with special expertise in the management of late radiation-induced bowel injury.

#### 4.1 Specific inclusion criteria

- i) Age over 18 years.
- ii) Past history of a malignant pelvic neoplasm (T1-4 N0-2 M0) of the rectum, prostate, testis, bladder, uterine cervix, uterus, vagina, vulva, anal canal or ovary.
- iii) A minimum 12 months follow-up post-radiotherapy (24 months for patients with past history of stage T4 and/or N2 disease).
- iv) A maximum 7 years post-radiotherapy.
- v) No evidence of cancer recurrence.
- vi) Gastrointestinal symptoms attributable to prior radiotherapy: grade 2 or higher in any CTCAE Version 4 category, or grade 1 with difficult intermittent symptoms.
- vii) Symptoms are not relieved by appropriate life-style advice and medication over a 3-month period after optimal gastroenterological assessment.
- viii) Physical and psychological fitness for Tocovid SupraBio + PTX therapy.
- ix) Written informed consent and availability for follow up.
- x) Willingness to keep to a specified level of dietary fat intake during the study.

#### 4.2 Specific exclusion criteria

- i) Surgery for rectal cancer.
- ii) Contra-indication or other inability to undergo magnetic resonance imaging, if required to rule out malignancy.
- iii) Dietary supplementation containing alpha-tocopherol above a daily dose of 30mg at any time during the last three months.
- iv) Medication with pentoxifylline at any time since radiotherapy.
- v) Pregnancy or breast feeding.
- vi) Ischaemic heart disease, uncontrolled hypertension, hypotension, acute myocardial infarction, cerebral haemorrhage, retinal haemorrhage, renal failure, liver failure and medication with insulin, ketorolac or vitamin K.
- vii) Allergy to soya.
- viii) Known hypersensitivity to the active constituent, pentoxifylline other methyl xanthines or any of the excipients', as per SmPC for pentoxifylline.

#### 4.3 **Pre-entry eligibility assessments**

All patients will undergo assessment by a medical specialist and research nurse in the Gastrointestinal Late Toxicity Clinic at The Royal Marsden. Eligibility requires that appropriate life-style advice after optimal gastroenterological assessment and a minimum 3-month period of standard medications are unsuccessful in completely controlling symptoms. Patients will have ample time to consider issues surrounding consent, which will be collected at the time of this appointment.

# 5 METHODS

#### 5.1 **Pre-treatment assessments**

The following must be completed *before randomisation*:

- i) Patient self-assessments using IBDQ, EORTC Quality of Life Questionnaires (QLQ-C30 & QLQ-CR29) and the Gastrointestinal Symptom Rating Scale.
- ii) Physician/Clinical Nurse Practitioner grading of late radiation-induced side effects using the modified CTCAE Version 4 form.
- iii) Completion of a 7-day food diary and an interview with the Royal Marsden dietetic team to ensure patients understand as far as possible how to maintain a stable fat intake.
- iv) Flexible sigmoidoscopy with rectal biopsies and medical photographs of rectal mucosa (patients who have received prostate brachytherapy will not be eligible for biopsy on grounds of safety). Biopsies will be taken in a standardised manner 8 cm from the anal margin\*. Mucosa and a minimal amount of submucosa will be sampled under direct vision. The size of the mucosal deficit caused by the biopsies is 2-3mm and in the patient with radiation proctopathy, this is minimally traumatic. Rectal biopsies (six in total) are optional and will be collected via endoscopy before Tocovid SupraBio+PTX/control therapy in as many volunteers as possible (target is 80% of the whole group). Biopsies will be taken from the posterior third of the rectum. 4/6 samples will be immediately snap frozen in liquid nitrogen for storage. 2/6 samples will be fixed in formalin for future immunohistochemical studies.
- v) Blood levels of IL6, TGF beta and MMP9 will be measured as markers of fibrosis. Analysis may be undertaken by researchers outside the Sponsor's organisation including collaborating institutions outside the EU. Any data transferred to a third party for future research will remain coded and will not contain any personal information.

\* A pilot study has confirmed that despite the small size of these superficial biopsies, informative samples containing mucosa and some submucosa are easily obtained from irradiated patients using this technique. In further preliminary experiments, we have established that two endoscopically directed biopsies taken from areas of the human rectum showing maximal change from previous radiotherapy are sufficient to obtain adequate amounts of RNA for further analysis.

### 5.2 Randomisation

Appropriate site staff at The Royal Marsden will randomise patients into the study by a telephone call to the Institute of Cancer Research Clinical Trials & Statistics Unit (ICR-CTSU) on [name]. The caller will be given the patient's unique identification number (Trial ID) and treatment allocation will be faxed/emailed to the Pharmacy Department. The Trial ID should be used on all Case Report Forms and all subsequent correspondence relating to that patient.

The following information will be required at randomisation:

- Patient's full name, hospital number, date of birth, NHS number.
- Name of hospital/department and person randomising patient.
- Confirmation that patient is eligible for the trial by completion of the eligibility checklist.
- Confirmation that the patient is free of active cancer.
- Confirmation that the patient has given written informed consent for randomisation on the Consent form.
- Whether or not the patient has given written informed consent for rectal tissue biopsies.
- Confirmation that the pre-treatment assessments listed in section 5.1 have been completed, by completion of Pre-randomisation checklist.
- IBDQ-B score (<60 or ≥60).
- Average daily fat intake (<90g or ≥90g).

# 5.3 Allocation of treatment

Treatment allocation will be in a 2:1 ratio of Tocovid SupraBio+PTX treatment: matched placebo and will be based on computer generated random permuted blocks. Patients will be asked to start their allocated treatment the day after randomisation. Pharmacy will be informed of the randomisation and hold records in the pharmacy file.

#### 5.4 Tocovid SupraBio + PTX therapy

#### 5.4.1 Treatment delivery

#### Treatment group

Tocovid SupraBio\* 200mg po bd plus pentoxifylline (PTX) 400mg po bd for 12 months.

*Control group* Matching placebos po bd for 12 months.

\*Combination of tocotrienols: d-gamma-tocotrienol + d-alpha-tocotrienol + d-delta-tocotrienol

#### 5.4.2 Monitoring of patients during treatment

- i) Adverse events will be recorded and reported as appropriate.
- ii) Any patient can be withdrawn from the study at any time.
- iii) Reasons for withdrawals and any adverse events will be documented and considered in the analysis.
- iv) Patients will be asked to produce a list of current medication (including dosage) before they enter into the study and to keep a medication diary during their Tocovid SupraBio + PTX/placebo therapy. Changes in medication during the 12

15

months of follow up will be collected at the assessment 24 months post randomisation.

- v) Levels of plasma GT3 will be measured at baseline, 3, 6, 9 and 12 months to confirm compliance with drug in those randomised to Tocovid SupraBio/PTX and undetectable levels of GT3 in those allocated placebo. Appropriate Royal Marsden site staff will check compliance in clinic from diary card kept by patients and any leftover trial medication (if applicable).
- 5.5 Follow up assessments during and after treatment (please see table below)
  - Patient self-assessments using IBDQ, the EORTC Quality of Life Questionnaires (QLQ-C30 & QLQ-CR29) and the Gastrointestinal Symptom Rating Scale 3, 6, 9, 12, 18 and 24 months after randomisation.
  - ii) Physician/Clinical Nurse Practitioner grading of late radiation-induced side effects using the modified CTCAE Version 4 form 3, 6, 9, 12 and 24 months after randomisation.
  - iii) Re-assessment with a 7-day food diary at 6 months and 1 year.
  - iv) Flexible sigmoidoscopy with rectal biopsies (optional) and medical photographs of rectal mucosa 12 and 24 months after randomisation.
  - v) Blood levels of IL6, TGF beta and MMP9 3, 6, 9, 12 and 24 months after randomisation as markers of fibrosis.

Procedure	Follow up (months post-randomisation)						
	3	6	9	12	18	24	
Patient self-assessment questionnaires	$\checkmark$	$\checkmark$	$\checkmark$	$\checkmark$	$\checkmark$		
CTCAE Version 4 grading	$\checkmark$	$\checkmark$	$\checkmark$	$\checkmark$		$\checkmark$	
Clinical assessments	$\checkmark$	$\checkmark$	$\checkmark$	$\checkmark$		$\checkmark$	
7 day food diary		$\checkmark$		$\checkmark$			
Rectal photographs				$\checkmark$		$\checkmark$	
Rectal biopsies (optional)						$\checkmark$	
Blood sample	$\checkmark$		$\checkmark$			$\checkmark$	

#### 5.6 **Processing and storage of tissue**

#### 5.6.1 Rectal tissue biopsies

Tissue samples a) snap frozen and stored in liquid nitrogen or b) fixed in formalin and embedded in paraffin blocks will be stored for future immunohistochemical analyses of blood vessel density and extracellular matrix components.

#### 5.6.2 Blood samples

Blood samples will be collected into EDTA tubes and stored to develop assays for novel markers of fibrosis.

# 5.7 Endpoints

# 5.7.1 Primary clinical endpoint

Change at 12 months in the bowel disease subset of the Modified IBDQ Quality of Life questionnaire.

# 5.7.2 Secondary clinical endpoints

- i) Change at 12 months in rectal IBDQ bleeding score between the two groups in those patients presenting with grade 2, 3 or 4 bleeding.
- ii) Change at 12 months in IBDQ faecal incontinence score between the two groups in those patients presenting with grade 1 or greater incontinence.
- iii) Proportion of items graded as marked or severe (grade 3 or 4).
- iv) Physician assessment of rectal dysfunction based on the modified CTCAE Version 4 grading.
- v) Patient self-assessments: QLQ-C30 and CR29 and the Gastrointestinal Symptom Rating Scale.
- vi) Photographic assessment of rectal mucosa.
- vii) Serum fibrosis marker levels.

# 5.7.3 Translational endpoints

- i) Rectal biopsies (optional)
  - Tissue samples will be banked until after the final analysis of the trial, when funding will be sought to identify molecular and cellular correlates of therapeutic response in the event of a statistically significant benefit for Tocovid SupraBio/PTX combination.
- ii) Blood samples Development of novel markers of fibrosis.

#### 5.8 STUDY MEDICATION

#### 5.8.1 Investigational Medicinal Product

The investigational medicinal products are as follows:

- i) Pentoxifylline 400mg capsules and Pentoxifylline matching placebo
- ii) Tocovid SupraBio 200mg capsules and Tocovid SupraBio matching placebo

Pentoxifylline tablets used will be sourced by Mawdsley Brooks Ltd, UK from member states of the EU. To maintain study blind, the EU licensed pentoxifylline tablets will be encapsulated and matching placebo capsules manufactured under EU GMP conditions by Mawdsley Brooks Ltd (or designated authorized manufacturing contractor).

Tocovid SupraBio soft gel capsules are considered a dietary supplement. Tocovid SupraBio capsules and matching placebo will be manufactured, packaged and labeled in accordance with EU GMP by Hovid Bhd, Malaysia. The manufacturing, packaging and labeling sites have been audited and assessed to ensure EU GMP compliance. An EU QP declaration equivalence to EU GMP for IMP manufactured by Hovid Bhd is provided with the trial application.

17

# 5.8.2 Preparation and Administration of Study Drug

#### Packaging & Labelling

All IMPs including placebos will be imported (where applicable), certified and released for use in this study by Mawdsley Brooks Ltd. IMPs will be packaged, labelled and dispatched to investigator site as agreed as open label supplies.

The Pharmacy department at The Royal Marsden will label study medication against prescriptions in accordance with requirements specified in Annex 13 of the Eudralex volume 4 and ensure that blinding is maintained.

#### Receipt of Drug Supplies

Drug supplies will be shipped directly to the pharmacy department. Upon receipt of the study treatment supplies, an inventory must be performed and a drug receipt log filled out and signed by the person accepting the shipment. It is important that the designated study staff counts and verifies that the shipment contains all the items noted in the shipment inventory. Any damaged or unusable study drug in a given shipment (active drug or comparator) will be documented in the study files.

#### Storage

Pentoxifylline/placebo and Tocovid SupraBio/placebo must be stored as per the product label. IMPs should be stored in the pharmacy and segregated from normal pharmacy supplies.

#### Blinding of Study Drug

Pharmacy will be unblinded in the study and will dispense appropriate IMPs as per randomisation confirmation received from ICR-CTSU (see section 5.2). All paperwork relating to identity of patients on active or placebo will be held in the pharmacy file, separate from the TMF held by the research team. Pharmacy will order supplies directly from Mawdsleys as per agreed process, without involvement from the investigator and research team.

#### Emergency Unblinding

In the case of emergency unblinding, the pharmacy department will hold a list of all patients registered onto study and treatment arm patients are randomised to. Pharmacy has a 24 hour oncall service and will be available to unblind in emergency situations as appropriate and as per local procedures.

#### Treatment Compliance

Patient's treatment compliance will be assessed by appropriate Royal Marsden staff in the clinic. Patients will be asked to bring all empty packaging/unused tablets at each clinic visit.

#### Drug Accountability and Destruction

The investigator will delegate responsibility for IMP management to the delegated pharmacist. Full drug accountability from receipt to destruction will be held in pharmacy for all IMPs. The delegated pharmacist will also ensure:

- IMPs are handled and stored safely and properly.
- IMPs are only dispensed to trial patients according to the protocol.
- IMPs will be destroyed (expired stock, patient returns, left over stock at end of study) as per local procedures in liaison with R&D and CI.
- Blinding of IMP prior to release to patient and research team.

## 5.8.3 Concomitant Medication

Disallowed medicines include:

- Ketorolac
- Insulin
- Vitamin K

Caution should be used with the following medicines in combination with pentoxifylline;

- Theophylline can lead to increased levels of theophylline therefore increased therapeutic drug monitoring required
- Anti-coagulants risk of increased anticoagulant activity
- Anti-hypertensives PTX may potentiate the effects of anti-hypertensive agents.
- Ciprofloxacin Concomitant administration with ciprofloxacin may increase the serum concentration of pentoxifylline in some patients. Therefore, there may be an increase in and intensification of adverse reactions associated with co-administration.
- Platelet aggregation inhibitors Potential additive effect with platelet aggregation inhibitors: Because of the increased risk of bleeding, the concomitant administration of a platelet aggregation inhibitor (such as clopidogrel, eptifibatide, tirofiban, epoprostenol, iloprost, abciximab, anagrelide, NSAIDs other than selective COX-2 inhibitors, acetylsalicylates (ASA/LAS), ticlopidine, dipyridamole) with pentoxifylline should be undertaken with caution.
- Cimetidine Concomitant administration with cimetidine may increase the plasma concentration of pentoxifylline and the active metabolite, lisofylline.

#### Dose Reductions

No dose reductions are permitted of any IMPs.

#### 5.9 Safety Reporting / Pharmacovigilance

#### 5.9.1 Definitions

#### Adverse Event (AE):

Any untoward medical occurrence in a patient or clinical trial subject administered a medicinal product and which does not necessarily have a causal relationship with this treatment. An AE can therefore be any unfavourable and unintended sign (including an abnormal laboratory finding), symptom, or disease associated with the use of a study drug, whether or not considered related to the study drug. Signs and symptoms of metastatic disease, as determined by the local clinical investigator, are not adverse events.

#### Adverse Reaction (AR):

All untoward and unintended responses to the study drug related to any dose administered. All AEs judged by either the reporting investigator or the sponsor as having reasonable causal relationship to a medicinal product qualify as adverse reactions i.e. an AR is possibly, probably or definitely related to the study drug. The expression reasonable causal relationship means to convey in general that there is evidence or argument to suggest a causal relationship.

#### Serious Adverse Event (SAE) or Serious Adverse Reaction (SAR):

Any untoward medical occurrence or effect which occurs within 30 days of the patient receiving study drug that at any dose:

- results in death: the patient's death is suspected as being a direct outcome of the AE.
- is life-threatening. Life-threatening in the definition of a serious adverse event or serious adverse reaction refers to an event in which the subject was at risk of death at the time of the event. It does not refer to an event which hypothetically might have caused death if it were more severe.
- requires hospitalisation, or prolongation of existing inpatient hospitalisation: admission to hospital overnight or prolongation of a stay in hospital was necessary as a result of the AE. Outpatient treatment in an emergency room is not itself an SAE, although the reasons for it may be. Hospital admissions/surgical procedures planned for a pre-existing condition before a patient is randomised to the study are not considered SAEs, unless the illness/disease deteriorates in an unexpected way during the study.
- results in persistent or significant disability or incapacity: the AE results in a significant or persistent change, impairment, damage or disruption in the patient's body function/structure, physical activities or quality of life.
- is a congenital anomaly or birth defect.

N.B. progressive disease and death due to disease are not considered SAEs but should be reported on the relevant forms (i.e. progression form for relapse and death form for death).

Medical judgement should be exercised in deciding whether other AE/ARs are serious. Important AE/ARs that are not immediately life-threatening or do not result in death or hospitalisation but may jeopardise the subject or may require intervention to prevent one of the other outcomes listed in the definition above, should also be considered serious and reported as such.

#### Suspected Unexpected Serious Adverse Reaction (SUSAR):

Any serious adverse event with a suspected relationship to study drug that is not listed on the SmPC (Pentoxifylline) / IB (Tocovid SupraBio) and is unexpected.

#### Causality

Many adverse events that occur in this trial, whether they are serious or not, will be known treatment related toxicities. The Chief Investigator is responsible for the assessment of causality of serious adverse events (see definitions of causality table). The drug manufacturer and/or other clinicians may be asked for advice.

Relationship	Description									
Unrelated	There is no evidence of any causal relationship with the trial									
	drug									
Unlikely	There is little evidence to suggest there is a causal									
	relationship (e.g. the event did not occur within a reasonable									
	time after administration of the trial medication). There is									
	another reasonable explanation for the event (e.g. the									
	patient's clinical condition, other concomitant treatment)									
Possible	There is some evidence to suggest a causal relationship (e.g.									
	because the event occurs within a reasonable time after									

#### Definitions for causality

CCR3894 Randomised double-blind controlled phase II trial of gamma-Tocovid SupraBio in combination with pentoxifylline in patients suffering long-term adverse effects of radiotherapy for pelvic cancer.

	administration of the trial medication). However, the influence							
	of other factors may have contributed to the event (e.g. the							
	patient's clinical condition, other concomitant treatments)							
Probable	There is evidence to suggest a causal relationship, and the							
	influence of other factors is unlikely							
Definitely	There is clear evidence to suggest a causal relationship, and							
	other possible contributing factors can be ruled out							

#### 5.9.2 Reporting procedures

Reporting of Serious Adverse Event (SAE) or Serious Adverse Reaction (SAR) Any SAE that occurs from the time of consent and up to 30 days following the last dose of the study medication must be reported. The Sponsor has delegated safety reporting to the Chief Investigator. Since this is a single-centre trial, the CI is also the PI. Any member of the research team who becomes aware of an SAE shall report the SAE to the CI using the SAE report form immediately and no later than 24 hours from site awareness of the event. The SAE will be assessed by the CI for causality and expectedness. The signed SAE form should be kept in the TMF. SAEs and SARs will also be recorded on the Sponsor's Pharmacovigilance Database in compliance with The Royal Marsden NHS Foundation Trust standard operating procedure for Pharmacovigilance gSOP-02.

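### Serious harm from the month-24 sigmoidoscopy or optional rectal biopsy falls outside both the SAE reporting window and the SAE definition

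*Protocol*

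**What the plan says.** - **Reporting window (5.9.2).** Any SAE "from the time of consent and up to 30 days following the last dose of the study medication must be reported". There is no filter on cause. Staff must report to the Chief Investigator within 24 hours of awareness, the Chief Investigator assesses causality and expectedness, and SAEs and SARs go on the sponsor's pharmacovigilance database.
- **Definition (5.9.1).** An SAE or SAR is an untoward occurrence "which occurs within 30 days of the patient receiving study drug that at any dose" meets one of the seriousness criteria. The time limit is part of the definition.
- **Treatment period (5.3, 5.4.1).** "Patients will be asked to start their allocated treatment the day after randomisation"; the active regimen is "200mg po bd plus pentoxifylline (PTX) 400mg po bd for 12 months", and the placebos run equally long.
- **Trial endoscopies (5.1, 5.5, schedule of events).** One is done before randomisation. After that: "Flexible sigmoidoscopy with rectal biopsies (optional) and medical photographs of rectal mucosa 12 and 24 months after randomisation". The table in 5.5 ticks biopsies at month 24 only, while the list in 5.5 and the schedule of events give months 12 and 24. All three agree on month 24.
- **Biopsy as a safety matter (5.1).** "patients who have received prostate brachytherapy will not be eligible for biopsy on grounds of safety". The same section describes the biopsies as causing little trauma.
- **Adverse event log (5.9.4).** All adverse events are logged and entered on the trial database, with no end date given.

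**The concern.** The trial carries out an invasive procedure in irradiated bowel roughly a year after its SAE rules have lapsed. If a patient bled or perforated and was admitted after the month-24 procedure, neither 5.9.1 nor 5.9.2 would make that event an SAE. The rapid report, the formal assessment and the sponsor's safety database would all be bypassed, although the protocol itself recognises biopsy as unsafe for one group of patients. The safety record of the month-24 procedure would then rest on the ordinary adverse event log alone.

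The two sections also appear to disagree at the other end of the window. Section 5.9.2 opens at consent, whereas 5.9.1 counts from receipt of study drug. The baseline endoscopy takes place before any drug is taken.

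**Working it through.** The plan gives no figure to reproduce; this is calendar arithmetic.

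**Inputs**
- First dose: day 1 after randomisation (5.3).
- Treatment: 12 months (5.4.1).
- Window closes: last dose + 30 days (5.9.2).
- Endoscopies: before randomisation, month 12, month 24 (5.1, 5.5, schedule of events).
- Assumed length of a month: 365.25 / 12 = 30.4375 days.

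**Window for a patient who completes treatment**
- Last dose: 1 + 12 × 30.4375 = day 366.25.
- Close: 366.25 + 30 = day 396.25, and 396.25 / 30.4375 = month 13.02.

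**Each endoscopy against the 5.9.2 window**

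| Endoscopy | Day | Position |
|---|---|---|
| Baseline | before day 0 | inside, provided consent came first |
| Month 12 | 365.25 | inside; 396.25 − 365.25 = 31 days of cover left |
| Month 24 | 730.5 | outside; 730.5 − 396.25 = 334.25 days, or 334.25 / 30.4375 = 10.98 months late |

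The share of the 24-month follow-up with no SAE reporting requirement is 334.25 / 730.5 = 45.8%.

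**Does another section close the month-24 gap?**
- 5.9.1: no. At month 24 the patient is about 12 months past the last dose, so the event fails the time limit in the definition. The paragraph on medical judgement widens the seriousness criteria, not the period.
- SUSAR reporting: no. It presupposes an SAE with a suspected relationship to study drug.
- 5.9.4: in part. The event can be logged, but the 24-hour report, the expectedness assessment and the pharmacovigilance database entry are specified for SAEs and SARs only.

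**Start of the window, side by side**
- 5.9.2: from consent. A serious complication of the baseline endoscopy is reportable.
- 5.9.1: within 30 days of receiving drug. That endoscopy precedes randomisation, and drug starts the day after randomisation. If the phrase means after a dose, the same event is not an SAE.

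**The case against.** The strongest reply is that little is actually hidden. The adverse event definition has no time limit and needs no link to drug, 5.9.4 logs every adverse event, and section 7.7.3 gives the IDMC side-effects and tolerability for all randomised patients plus any analysis it requests. A month-24 bleed can therefore be recorded and can reach the IDMC. This stands. What is lost is SAE handling and the SAE route to the sponsor's database, not every trace of the event.

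A reader might infer that harm from trial procedures is never reportable. The documents do not support that. Section 5.9.2 covers SAEs of any cause from consent, so the baseline endoscopy is covered, as is the month-12 endoscopy in patients who complete treatment.

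A reader might also infer that patients who stop drug early lose cover for the month-12 endoscopy. On the arithmetic this would need a stop before about month 11 ((365.25 − 30) / 30.4375 = 11.01) with continued attendance. Section 7.5 speaks of withdrawal from the study for toxicity or non-compliance, and the protocol does not clearly say that such patients still have that endoscopy. The point is not established.

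On the start of the window, the 5.9.1 phrase does not say after a dose, so an event shortly before the first dose could be read as within 30 days of it. That reading is open. It makes the conflict one of wording and does not show that baseline harm escapes reporting.

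Finally, the sponsor's pharmacovigilance procedure cited in 5.9.2 is not at hand and might go further. The protocol's own rule would still need to say so.

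**Conclusion.** The point holds in a narrow form. Serious harm from the month-24 sigmoidoscopy or optional biopsy is outside both the reporting window and the SAE definition, by about 334 days for a patient who takes drug for the full 12 months. No other section of the protocol brings it back into SAE handling. The differing start points in 5.9.1 and 5.9.2 are a separate, smaller inconsistency that needs reconciling.

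The number of patients exposed cannot be fixed from the protocol. It is tempting to apply the 80% biopsy target and the six samples per patient to the 117 recruits, but 5.1 states both for the pre-treatment biopsies only, and 117 already includes a 15% drop-out allowance. No procedural complication rate is given either.

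The result assumes that the planned last dose is at about month 12, that visits occur on schedule, and that consent precedes the baseline endoscopy. It is a gap worth closing because it concerns an invasive trial procedure and costs little to close. It does not bear on the primary efficacy analysis.

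**What to change.** Reconcile 5.9.1 and 5.9.2 into one definition used in both places: SAEs are reportable from consent to 30 days after the last dose, and also for a stated period, for example 30 days, after any later trial endoscopy or biopsy, including month 24. Take the time limit out of the SAE definition or make it identical to the reporting rule.

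The cost is amendment wording and a few more SAE reports.

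Two additions are optional. One is a separate entry on the SAE form for relationship to a trial procedure, since the causality scale addresses only the trial drug; the scale does not itself block reporting. The other is a telephone check 30 days after the last dose, since after month 12 the next scheduled contacts are the month-18 questionnaires and the month-24 visit. Neither is needed to close the gap.
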